**Short study title: “Postpartum Family Planning” or “Postpartum FP”**

## **I. Background**

Ensuring adequate birth spacing could prevent an estimated 9% of deaths worldwide among children less than 5 years of age. Many women, though, are not protected against repeat pregnancy. An estimated 61% of women in their first year postpartum do not want a repeat pregnancy and yet are not using contraception. The lactational amenorrhea method is effective as temporary contraception for breastfeeding women, but its duration of protection varies substantially, and women often fail to start another method before fertility returns. Furthermore, many women do not adhere to their lactation intentions: in a U.S. study, almost one-third of women who stated an intention to breastfeed either did not start or stopped within 6 weeks of birth.

Intramuscular injectable depot medroxyprogesterone acetate (DMPA) is rapidly becoming the contraceptive of choice in some settings, including regions where high maternal and child mortality make birth spacing particularly critical. **Advisable timing of DMPA initiation among breastfeeding mothers, though, is in dispute.** Progestin potentially could interfere with lactogenesis, milk quality or supply, overall duration, or infant growth. While human studies have not identified substantial effects from this exposure on breastfeeding outcomes, they suffer from low power and various possible biases. Given the theoretical risks, the World Health Organization (WHO) advises against use of progestin-only injectables during the first six weeks post-partum among breastfeeding women. In contrast, in its guidance for the U.S., the Centers for Disease Control and Prevention (CDC) recommends that progestin-only injectables generally can be started immediately postpartum on the grounds that their known advantages, as a whole, outweigh their unknown risks. **This inconsistency in guidance reflects the lack of high-quality data for making evidence-based decisions.**

Balancing theoretical risks of harm against known risks of rapid repeat pregnancy has led to contradictions in clinical guidance and practice. While U.S. guidelines permit immediate postpartum DMPA use among breast-feeding women, the practice often is restricted in clinical settings in the U.S. and globally due to concerns ungrounded in rigorous science.

## **II. Study Summary**

**We will conduct a randomized controlled trial (RCT) to evaluate the effects of immediate postpartum initiation of DMPA on breastfeeding and long-term contraceptive use.** We will enroll approximately 800 adult women who have delivered a healthy, full-term infant at a participating hospital, who intend to breastfeed for  $\geq 6$  months, and who want to use DMPA (Depo-Provera; Pfizer Corp.) We will randomize women to **receive within 48 hours of delivery: 1) DMPA (“intervention” arm), 2) placebo injection (“placebo” arm) or 3) no injection (“open control” arm).** The first two arms will be blinded while the open control arm will be unblinded. Note that postpartum patients at the study site do not receive DMPA before discharge as standard care. At enrollment, women will receive condom counseling and provision and referral for contraception at 12 weeks (intervention and placebo arms) or at 6 weeks postpartum (open control arm). We will collect data on lactogenesis, infant feeding and growth, and contraception use during 12 follow-up months. We conducted a pilot study (N=100) in the target population at OSU, which supports the feasibility of the current trial.

## **III. Objectives**

**Objective 1: To determine the effect of immediate postpartum initiation of DMPA on breastfeeding.** We hypothesize that administration of DMPA immediately postpartum (i.e., before hospital discharge) will not impair breastfeeding compared to administration beginning at 12 weeks post-delivery. To increase the likelihood of detecting a negative effect if one exists, we will evaluate the primary outcome, timing of lactogenesis stage II (onset of copious milk secretion, usually occurring within 96 hours postpartum), as well as a range of secondary outcomes: breastfeeding duration, perceived need for supplementation, use of supplementation, perceived adequacy of milk production, and infant anthropometric measures, including body composition with whole-body air displacement plethysmography (OSUWMC site only). Sensitivity analysis will evaluate 1) excluding women in the open control arm and 2) determining whether the findings differ by race.

**Objective 2: To determine the effect of immediate postpartum initiation of DMPA on contraception use.** We hypothesize that putative DMPA use (i.e., blinded assignment to intervention or placebo arms) will put women on a better trajectory of contraception use by intervening during a time when they likely are highly motivated to avoid pregnancy. In contrast, women who are assigned to start DMPA after a delay risk losing motivation to initiate use. To test this hypothesis, we will compare prevalence of use of a highly-effective contraceptive method at 12 months post-delivery between women in the intervention and placebo arms versus the open control arm. Secondary outcomes will include DMPA use at 12 months. Sensitivity analyses will evaluate 1) whether the findings differ by race and 2) whether the findings differ after restricting the intervention and placebo arms to the subset of women who believe that they were in the intervention arm.

#### IV. Literature

##### A. Literature in Support of Objective 1: The relationship between immediate postpartum initiation of DMPA and lactation.

Because delayed lactogenesis stage II is associated with a range of poor breastfeeding outcomes (failure to initiate, reduced duration, and use of supplements), identifying any negative effect of progestin on lactogenesis would be important. In theory, progestin could inhibit the process. Production of progesterone by the adrenal glands, ovaries and placenta increases during pregnancy. Plasma progesterone levels do not decrease until after delivery of the placenta, after which time, levels decline rapidly, reaching follicular phase levels after 2-3 days. This decline, along with decreased estrogen levels and infant suckling, is thought to trigger lactogenesis. Cases of placental retention, in which lactogenesis has been delayed up to three weeks, support this physiologic mechanism. Also, exogenous progesterone given around the expected parturition time in rats or after fetus removal in ewes inhibits milk secretion; in contrast, no inhibitory effect occurred in rat models when progesterone was given after the establishment of lactation. Note, though, that progesterone and the synthetic progestogen, medroxyprogesterone acetate, used in the contraceptive injectable are different compounds, which are known to produce different effects in women; thus, **findings from trials on progesterone use in animals are suggestive but cannot be assumed to represent the effects of DMPA use in women.**

**A recent systematic review found no RCTs in humans on the effect of immediate postpartum initiation of DMPA on lactation.** Three RCTs compared immediate postpartum use of a progestin-only method other than DMPA with the initiation of the same or a different hormonal method later during the puerperium. The three trials made the following comparisons: etonogestrel implant used immediately postpartum versus DMPA at 6 weeks postpartum;

levonorgestrel IUD placed postplacentally versus at 6-8 weeks postpartum, and etonogestrel implant placed at 1-3 days versus at 4-8 weeks postpartum. Three additional RCTs compared initiation of a progestin-only method within 48 hours postpartum – norethisterone enanthate injectable, etonogestrel implant, or daily oral administration of 0.350 mg of norethindrone -- versus placebo. The trial of the levonorgestrel IUD did not find differences between study arms in breastfeeding initiation or continuation at 6-8 weeks but did find that the postplacental arm had less breastfeeding continuation at 6 months. The remaining five trials found no differences in lactation outcomes between groups. Overall, the six trials were small (20-166 participants) and had short follow-up intervals (2-26 weeks). **Consequently, evidence from the trials is insufficient for ruling out an inhibitory effect from progestin. Furthermore, the trials are non-informative regarding the effect of immediate initiation of DMPA specifically,** as this involves a different type of progestin given through a different route of administration, and involving a larger loading dose of progestin.

**Non-randomized evidence regarding the effect of immediate postpartum DMPA exposure on lactation outcomes is inconclusive.** Ten observational studies compared breastfeeding outcomes between women choosing to use DMPA starting within the first 6 weeks postpartum compared to women using another or no method. In six of these studies, the upper window for starting DMPA ranged from five days to four months postpartum. None of these studies found impaired lactation outcomes (and three found DMPA to be associated with increased breastfeeding duration). However, because women in the six studies received DMPA after the typical window for lactogenesis stage II, their findings do not shed light on the potential effects of DMPA initiated before hospital discharge. The remaining four observational studies evaluated the effects of earlier DMPA administration, specifically 1-2 days postpartum, within 72 hours postpartum, or at the time of or before hospital discharge. These study findings were mixed in that early DMPA administration was associated with longer mean breastfeeding duration; with less breastfeeding continuation at four weeks or at three months; or with no difference in duration. Furthermore, these non-randomized studies do not support firm conclusions because 1) they did not control for potential confounders related to women choosing to start DMPA use, which could have introduced substantial bias, and 2) they did not employ standardized, validated outcomes.

**No study on DMPA use during breastfeeding has assessed infant adiposity, specifically, as part of a more comprehensive assessment of growth.** Increased infant weight gain typically has been interpreted in the breastfeeding and DMPA literature as a positive outcome. However, early hormone exposure theoretically could promote adiposity at the expense of other growth, such as brain and lean mass. Also, excessively rapid infant weight gain, in general, is associated with lifetime cardiovascular risk and is an early indicator of obesity risk. Five cohort studies measured the effect of postpartum DMPA exposure on infant weight gain. The first study (N=331) comparing initiation of DMPA or norethisterone enanthate at either 7 or 42 days postpartum to a non-hormonal comparison arm found no difference between groups in infant weight gain in first three months. However, during months 4-6, infants in the two injectable arms had higher weight gain than those in the comparison arm. The four other non-randomized trials that evaluated infant growth found no difference in weight gain among breastfeeding infants of mothers using DMPA compared to infants in a comparison arm not using DMPA over six months, a mean of 18 months or 4.5 years, or a maximum of 17 years of postpartum follow up. Again, in these non-randomized studies the failure to control for important confounders related to women self-selecting use of DMPA precludes any firm conclusions. Furthermore, despite the assumption in these studies that increased weight gain is a positive outcome, the validity of this interpretation is unknown. By measuring adiposity, we will have a superior measure of the effect of the exposure.

**In summary, an inhibitory effect on breastfeeding from immediate postpartum administration of DMPA cannot be ruled out due to the lack of data from RCTs conducted in women, the failure to use validated measures of lactation and the reliance on crude measures of infant growth and adiposity. The data have important limitations:** short follow-up intervals, low power, lack of consistency in using sensitive and standardized outcome measures, and the lack of RCTs evaluating DMPA administration specifically in the immediate postpartum period.

**B. Literature in Support of Objective 2: The relationship between immediate postpartum initiation of DMPA and contraception use.**

Unmet need for contraception remains high among postpartum women. An analysis of Demographic and Health Surveys conducted in 21 low- or middle-income countries found that 61% of postpartum women did not want to become pregnant in the next year but were not using contraception. Likewise, data from the 2006-2010 National Survey of Family Growth found that 35% of pregnancies in the U.S. were conceived within 18 months of a previous birth, putting both the woman and fetus at risk of adverse perinatal outcomes.

Interactions with the healthcare system around the time of childbirth could represent an important window for intervening as women often are highly motivated to initiate contraception use to prevent a closely-spaced, repeat birth. Consequently, the WHO recommends that postpartum women be offered contraceptive counseling and provision following delivery before discharge, and professional bodies in the U.S. (e.g., the American College of Obstetricians and Gynecologists and the American Academy of Pediatrics) advise that prenatal and postpartum care include discussion of contraceptive options and initiation of postpartum contraception. Prenatal and postnatal contraception counseling, though, often are not available or are not offered. Contraception counseling is particularly important for women who want to start a new method. Changing method type is common during the postpartum period, with women citing a desire for avoiding repeat births, having improved method reliability, or avoiding safety concerns for the mother or infant.

Interventions delivered immediately postpartum as well as integrating postpartum contraception counseling into immunization and child health services have been shown to increase postpartum contraception use. In contrast, recent Cochrane reviews revealed inconsistent evidence on whether providing counseling on postpartum contraception reduces unmet need or repeat pregnancy rates. However, the quality of evidence on effectiveness of the interventions included in the Cochrane reviews was generally low, and the authors argued that more rigorous trials are needed to determine the effects of the timing and elements of postpartum contraception counseling on contraception use and unintended pregnancy rates.

RCTs have shown that a “quick start” of combination hormonal contraception (i.e., starting on the day of the health care visit) can increase contraceptive use compared to the conventional start (i.e., delaying start until the beginning of the next menstrual cycle). The increase in contraception use from the quick start, though, appears to wane over time. However, these findings cannot be assumed to be informative as to the effects of proposed intervention. First, postpartum women could be expected to have different motivation to initiate contraception than a more general population of women. Furthermore, the quick start studies differed from the current trial in that women did not need to return for care to start their method. That is, they either initiated the combination oral contraception or the contraceptive patch immediately or were provided the method to take with them to start later. Finally, these studies did not involve the use of DMPA, which would have required the women assigned to the conventional start to

have returned to the clinic for the method. Postpartum women have substantial new demands on their time that might make it especially difficult for them to return to a facility to obtain contraception during the early postpartum interval.

**To date, no RCTs have examined the effect of immediate postpartum provision of DMPA on contraception use.** Administering the method at a time when women are highly motivated to avoid repeat pregnancy could help overcome any initial reluctance to start the method and could put women on a better trajectory of contraception use following delivery. While women often discontinue use of methods, including DMPA, a substantial proportion might be motivated to continue to use DMPA. On a population level, this could have huge implications for avoiding adverse consequences of repeat pregnancies. However, no evidence on this is available.

### **C. Evidence from Preliminary Studies**

From September to November 2015, we conducted a pilot study at one of the sites for the current trial, namely, the Labor and Delivery Unit at OSUWMC. We interviewed, before their hospital discharge, 100 postpartum women in the target population (i.e., English-speaking women  $\geq 18$  years of age who delivered a term, healthy infant of  $\geq 2500$  grams and who intended to breastfeed for  $\geq 6$  months). Nineteen percent of survey participants stated that they would “definitely” or “probably” start DMPA before discharge if they were offered the opportunity. The most commonly cited reasons for unwillingness to join the hypothetical trial were the need for more information on DMPA and more time to consider their contraceptive plans. Although professional associations in the U.S. recommend that prenatal visits include contraceptive counseling, almost half (43%) of the participants in this preliminary survey reported not receiving such counseling during prenatal care. Concerns about potential effects of DMPA on lactation did not appear to factor into women’s willingness to use DMPA; among those not interested in starting DMPA, only 2% cited concerns about its effects on their breastfeeding infant. Patients also had limited knowledge regarding the methods that are recommended for use during the first six weeks postpartum while breastfeeding. Among women who indicated a willingness to immediately start DMPA, 94% reported being willing to participate in a hypothetical trial that involved completing questionnaires online, and 76% reported being “definitely” or “probably” willing to be randomized to start the method either before discharge or at a later time. Among respondents wanting to start DMPA but indicating a lack of willingness to join the hypothetical study, women cited barriers, such as inconvenient campus parking for returning for follow-up visits.

[figure not shown]
Large numbers of eligible women are available to recruit for the current trial. A review of OSUWMC patient records revealed 3,929 uncomplicated deliveries of term, singleton infants of  $>2500$  grams without any apparent health problems delivered to adult, English-speaking women during 2015. We previously found that 76% of English-speaking, adult women who delivered a singleton, live-born infant at OSUWMC during a five-month interval in 2011 intended to breastfeed their infant. This finding is consistent with a population-based survey in 2014-2015 that found 78% of newborn infants in Ohio initiated breastfeeding. Thus, we estimate an annual expected caseload at the OSUWMC study site of 2,986-3,064 adult, English-speaking women who deliver a term, singleton, healthy infant of  $\geq 2500$  grams and who intend to breastfeed their infant. Over the planned 30 months of study enrollment, we would only need to enroll 5.6%-5.7% of eligible women in this group to meet the target sample size. Note that this is well below the 14.4% of breastfeeding women in the pilot study who wanted to immediately start DMPA and were willing to be randomized to the timing of initiation. **Thus, preliminary data support the feasibility of the trial by demonstrating the adequacy of the patient caseload at the enrollment site, OSUWMC.**

## V. Procedures

### A. Overview

We will conduct an RCT of 429 women and their infant per arm (Figure 1). We will promote the study and enroll eligible, consenting women 1) prenatally at the primary obstetrical facilities that refer to the study sites for delivery; 2) prenatally at pregnancy-related classes in the community or 3) postpartum at a participating hospital after their delivery and before their discharge. We will enroll approximately 800 women because we anticipate a high number of screening failures before randomization. Our power is based on having approximately 143 women-infant pairs randomized to each of the three arms.

**Figure 1. Study design**

The study will be partially blinded: participants and study staff, including the study statistician, will be blinded as to the assignment for those in the intervention and placebo arms. In contrast, no one will be blinded as to assignment to the open control arm. (Note that it is not feasible to maintain blinding for the open control arm even among the data analysts given the planned grouping of the arms for the data analyses.) DMPA has a duration of protection of 12 weeks. Women in the intervention or placebo arm will be counseled to refrain from initiating hormonal contraception in the next 6 weeks and to refrain from initiating DMPA in the next 12 weeks. Study staff will use the "Contraceptive choice information sheet" to explain the contraceptive methods that participants can use depending on whether they are assigned to an arm that receives a shot or the arm that does not receive a shot. All participants will be counseled to use condoms post-delivery to avoid a repeat pregnancy (as they either received no shot or could have received a placebo shot). Participants will receive a supply of condoms for either 12 weeks (intervention or placebo arm) or 6 weeks (open control arm), and will be referred to receive DMPA at either 12 weeks (intervention or placebo arm) or 6 weeks post-delivery (open control arm).

Data collection, which will occur at enrollment and through 12 months of follow up, will involve 1) questionnaires on demographics, characteristics and behaviors, lactogenesis, breastfeeding and contraception use and 2) infant anthropometric measures (Table 1).

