**Table 1. Data collection by objective, location, schedule and mode of collection, and compensation.**

Objective	Data collection	Location	Schedule and mode of collection	Compensation
1,2	Enrollment Questionnaire	Participating hospital	Self-administered within 48 hrs of delivery	\$80 in cash at OSUWMC; \$80 in electronic gift card at Emory-affiliated Hospital
1	Milk Let-Down Questionnaire	Participating Hospital / text, telephone, email	Interviewer administered ≤3 times daily in person at OSUWMC or Emory-affiliated hospital, then daily via text, telephone or email during the first 7 days postpartum until lactogenesis stage II occurs	One payment of \$30 in electronic gift card at all sites
1,2	Follow-up Questionnaire	Online	Self-administered at 1, 2, 4, 6, 9 and 12 months. Questionnaires at 1, 6 and 12 months include infant anthropometric measures* from well-child visit data	\$10 per interview in electronic gift card at all sites
1	Infant adiposity (PEA POD) and other infant measures*†	OSUWMC only	Measured by trained study staff at 4 months of age	\$40 in gift card, a branded gift (e.g., a cell phone popsocket or a pen with light) worth less than \$4.00, and either parking pass or transportation by cab to appointment

OSUWMC = Ohio State University Wexner Medical Center; \*Includes weight, length, head circumference; †Visit not completed by participants who delivered at an Emory-affiliated Hospital

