**Table 2. Location for recruitment, screening and enrollment by prenatal and postpartum status and type of location**

Women	Type of location	Location
Prenatal	Prenatal care at primary obstetrical facilities that refer to a participating hospital for delivery	
 
• Hospital obstetrics-gynecology outpatient clinic
 
• Faculty practices
 
• Primary One health centers
 

	Local classes for pregnant women in the community	
 
• Lactation, birthing and prenatal yoga classes
 

Finally, secondary outcomes will include infant measures collected during the follow-up questionnaire (using maternal reports of data from well-child visits) and during the 4-month visit at OSUWMC. Participants enrolled at an Emory-affiliated hospital will not complete a 4-month visit because the site lacks the ADP system. The latter will include the following: 1) percent fat mass (%FM) and fat-free mass (FFM%) measured using the validated, non-invasive whole-body air displacement plethysmography (ADP) system; 2) length with a SECA 416 digital infantometer; 3) head circumference with metric tape; 4) body weight with SECA 727 digital scale; and 5) skinfold with Holtain calipers. We will ensure consistently high-quality measurement by regular monitoring, assessing reliabilities, and refresher training.	Postpartum	Through MyChart Hospital	
 
• Tour of study hospitals during pregnancy
 
• OSUWMC and participating Emory-affiliated hospitals
 

---	------------	--------------------------	---

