Participants will be referred for DMPA at 12 weeks if in the intervention or placebo arms and at 6 weeks if in the open control arm. Participants will receive referrals for financial assistance for DMPA as appropriate. Participants will be counseled to use condoms for all sexual intercourse before receiving DMPA and will receive a supply of condoms for 12 weeks (intervention or placebo arms) or 6 weeks (open control arm). Interviewers will administer the short “Milk Let-Down Questionnaire” up to three times daily in person before discharge or until lactogenesis II occurs.

**Follow up.** If lactogenesis II does not occur before hospital discharge, participants will be asked to complete the “Milk Let-Down Questionnaire” daily via telephone, text or email for the first 7 days postpartum until the event occurs.

Participants will be instructed to complete an online “Follow-up Questionnaire” at 1, 2, 4, 6, 9 and 12 months post-delivery. The “Follow-up Questionnaire” will collect data on breastfeeding behaviors and perceptions; contraception use; and infant physical measurements from well-child visits. If the participant does not have the information from her infant’s well-child visit on-hand or if the information that she provides is incomplete or appears to be inaccurate, we will extract the data on the infant’s weight, length and head circumference from the medical records at their pediatrician’s office.

Participants enrolled at OSUWMC will be asked to return with their infant to OSUWMC for a four-month visit, during which infant measures will be collected (infant adiposity via PEA POD, weight, length, head circumference and skinfold) and recorded on the “Four-month Visit Form.” If women have not already completed their 4-month online “Follow-up Questionnaire” at the time

of the in-person visit, they will be instructed to do so using a computer established for this purpose at OSUWMC.

**Compensation.** Participants will receive compensation (amounts specified in Table 1) for their time and travel expenses. The compensation amounts are in-line with recent research with similar populations.

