**Blinding.** Blinding of the investigational product is critical to the integrity of the study. Participants and study staff will be blinded to the study drug assignment to the intervention and placebo arms. The Investigational Drug Services (IDS) Pharmacy at the study sites will have responsibility for organizing the blinding and preparing the injections. The IDS Pharmacy provides support to clinical trials at the study site and operates in compliance with all relevant regulatory and institutional policies. An unblinded pharmacist will prepare the injections in such a way as to ensure the masking of the contents of the syringe. The three study arms will receive the following: 1) intervention arm will receive DMPA injection; 2) placebo arm will receive 0.9% sodium chloride injection; and 3) open control arm will receive no injection. After completion of randomization and treatment allocation, study medication (i.e., DMPA injection or 0.9% sodium chloride injection) will be withdrawn into a 1mL syringe. Syringes will be masked using amber tinted tape to ensure blinding (see Figure 2).

**Data collection and management.** All study data will be recorded into the PHI version of the electronic data capture system, REDCap. Supported by the OSU Center for Clinical and Translational Science (CCTS), REDCap facilitates the transmittal of secure, encrypted and password-protected data. CCTS will program the data entry screens (with audio component options for participant-administered questionnaires), implementing built-in skip patterns and quality control checks. Data will be instantaneously uploaded behind the secure OSU firewall. The PI will monitor data during the study to resolve potential issues upon detection.

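### The plan waives masking to the open-control arm for the staff who take the 4-month infant measurements, and gives no reason that applies to them

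*Combined protocol and SAP*

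**What the plan says.** Section V.A (text under Figure 1) masks the intervention and placebo arms from participants and staff, then exempts the third arm for every role: "In contrast, no one will be blinded as to assignment to the open control arm". The reason given is that "it is not feasible to maintain blinding for the open control arm even among the data analysts given the planned grouping of the arms". The Blinding paragraph of section V.D has the same scope: "Participants and study staff will be blinded to the study drug assignment to the intervention and placebo arms".

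Table 1 describes the OSUWMC-only infant visit as "Measured by trained study staff at 4 months of age". Section V.C lists its measures. Percent fat and fat-free mass are "measured using the validated, non-invasive whole-body air displacement plethysmography (ADP) system", weight is by digital scale, and length is by digital infantometer. Two measures are manual: "head circumference with metric tape" and "skinfold with Holtain calipers". Section V.C also promises monitoring, reliability assessment and retraining. No section provides for a measurer who does not know the arm.

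Section V.E pools placebo and open control as the comparator for the primary outcome. For secondary outcomes it specifies t-tests or chi-squared tests without restating the grouping. Section III lists infant anthropometry and body composition under Objective 1 and makes exclusion of the open-control arm a sensitivity analysis.

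**The concern.** The waiver is a stated rule, and its justification is analytic. An analyst who must combine two arms will see which women had no injection. A person holding calipers months later has no such need.

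Reliability checks and retraining control operator variation, but they do not remove expectation: a measurer can be consistent and still read one group slightly differently. If that happens in open control alone, the error does not cancel in a comparison of DMPA with placebo and open control combined.

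Section IV.A criticises earlier studies for crude growth measures and raises the possibility that hormone exposure promotes fat at the cost of other growth. Skinfold, head circumference and length bear on that question. A biased comparator could create a difference or hide one.

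**Working it through.** **1. The plan's own figures.** Inputs from section V.E: margin 6 h, SD 18 h, two-sided 95% CI, 143 per arm. Power = Φ(6/SE − 1.96).

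- Intervention vs pooled comparator: SE = 18 × √(1/143 + 1/286) = 1.844; 6/1.844 = 3.255; power 90.2% (stated 90%).
- With 10% missing: SE = 18 × √(1/128 + 1/256) = 1.949; power 86.9% (stated 87%).
- Intervention vs placebo: SE = 18 × √(2/143) = 2.129; power 80.5% (stated 80%).

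These agree, which confirms a comparator of 2 × 143 = 286 for the primary outcome. The documents give no power or sample size for the 4-month measures.

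**2. Share of the comparator.** 143/286 = 0.5. If readings in open control shift by b (in SD units) and the other arms do not, the pooled comparator mean moves by b/2.

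**3. Grouping for secondary outcomes.** Section V.E does not restate it. Section III makes dropping open control a sensitivity analysis for Objective 1, so the natural reading is that the main analysis includes that arm. This is an inference.

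**4. Illustrative effect on the false-positive rate.** With n infants per arm, SE = √(1/n + 1/(2n)) = √(1.5/n). With δ = (b/2)/SE, the two-sided rejection rate when there is no true difference is P(Z > 1.96 − δ) + P(Z < −1.96 − δ). The small extra variance from mixing two comparator means is ignored.

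Both b and n are assumptions. The value n = 143 means every infant is at OSUWMC and attends. The value 114 borrows the 20% attrition that section V.E assumes for 12 months. Lower values allow for Emory-affiliated participants, who have no such visit, and for missed visits.

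| Infants per arm | SE (SD) | b = 0.1 | b = 0.2 | b = 0.3 |
|---|---|---|---|---|
| 143 | 0.102 | 7.8% | 16.4% | 31.0% |
| 114 | 0.115 | 7.2% | 14.1% | 25.8% |
| 80 | 0.137 | 6.5% | 11.3% | 19.5% |
| 57 | 0.162 | 6.1% | 9.5% | 15.2% |

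Example, n = 114 and b = 0.2: δ = 0.10/0.1147 = 0.872; P(Z > 1.088) + P(Z < −2.832) = 14.1%.

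**5. The planned check.** Intervention vs placebo excludes open control and so excludes the shift. Its SE is √(2/n). An effect that the pooled contrast detects with 80% power lies 2.80 pooled SEs from zero. In the smaller contrast it lies 2.80 × √(1.5/2) = 2.43 SEs from zero, giving power Φ(2.43 − 1.96) ≈ 68%.

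**The case against.** The strongest reply is that the trial already holds an unbiased comparison. Intervention and placebo are masked from participants and staff, and Section III plans an Objective 1 analysis without open control. That stands, and it limits the harm. It remains a sensitivity analysis with less power, and it does not correct the pooled estimate.

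Second, the adiposity measure that the protocol stresses comes from plethysmography, and weight and length come from digital instruments. This largely stands. Length still depends somewhat on positioning, so what remains is skinfold, head circumference and, in part, length, at one site.

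Third, mothers know whether they had an injection, and staff who enrolled them may remember. That stands too, and it means masking can only be partial.

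A reader might go further and infer that record replacement is also biased, because growth data are taken from pediatric records "if the information that she provides is incomplete or appears to be inaccurate". The documents do not support this. They do not say who makes that judgement or whether that person sees the arm, and the same rule covers all arms.

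**Conclusion.** The point holds for the manual 4-month measures. The masking waiver reaches the measurers, its stated reason does not, and the arm concerned is half of the pooled comparator (for secondary outcomes, on the implied grouping). The change is worth making; it does not call the trial's main conclusion into question.

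The range of about 6% to 31% is conditional on the assumed shift and attendance. Four stronger readings are tempting and not supported:

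- That these are safety outcomes. The documents class them as secondary, although they bear on possible infant harm.
- That a bias is expected, or that it favours a finding against DMPA. Neither size nor direction can be derived. The stated hypothesis is no impairment, so expectation could equally pull readings towards no difference.
- That the primary outcome is affected. Time to lactogenesis II is reported by the mother in the first week and does not come from these measurers.
- That masking costs almost nothing. The documents contain no staffing plan from which to judge that.

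**What to change.** Reword section V.A so that the absence of masking to open control covers participants, pharmacy, enrolling and counselling staff, and analysts only. For the 4-month visit:

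- hide the arm from measurers in REDCap and use a form that carries only the PIN;
- take the measurements before any discussion of contraception;
- ask mothers not to mention their group, and record any disclosure;
- where existing staffing allows, use a measurer who did not enrol or counsel that woman.

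State in section V.E which arms are compared for the secondary outcomes, and report intervention vs placebo alongside the pooled result for the 4-month measures.

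The cost is a restricted REDCap view, a revised form and visit-script wording. No sample size or power figure changes. No staff need be added where someone who did not enrol or counsel the woman is already available. Some mothers will disclose and some staff may recall the arm, so the bias would be reduced and not eliminated.
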